1.0 BACKGROUND AND HYPOTHESES

Although Parkinson's disease (PD) has been mainly viewed as a movement disorder, the pathophysiology of declined motor function incorporates impairments of multiple systems (sensory, motor, and cognition). Specifically, it has been demonstrated that cognitive function may play an essential role in daily motor function for individuals with PD^{1,2}. Cognitive dysfunction involving set-shifting and attentional control has been found to be associated with movement slowness in performing a finger sequence task and freezing of gait^{3–8}. The above results are in line with the clinical observations that motor performance in individuals with PD is degraded when the cognitive load of motor tasks increases, such as talking on the phone while walking or maneuvering between people in a crowded mall. Furthermore, a recent rodent model indicates that cognitive dysfunction may occur prior to the onset of motor symptoms⁸. Human studies also show that 25-30% of individuals with PD exhibit cognitive impairments at the time of diagnosis ^{9,10}. The overall evidence suggests that cognitive dysfunction may contribute to degraded motor function.

Interestingly, emerging evidence demonstrate that aerobic exercise and resistance training can improve cognitive function in individuals with PD^{11–15}. One study done by Ridgel et al. (2009) shows enhanced cognitive function after 30-min passive cyclying¹². The findings indicate that there is a tight interplay between motor and cognitive function in individuals with PD. Therefore, targeting cognitive function and incorporating cognitive training into physical rehabilitation may be important as it may better help individuals with PD to transfer the learned skill into real-world daily activities. Although there is mounting evidence for the benefits of physical exercise in PD, few studies investigate whether combining cognitive training with physical exercise can provide additional benefits than physical exercise alone.

It has been suggested that exercise exerts its beneficial effects in PD, at least partially, through changes in the brain 16. However, few studies have linked these improvements in motor and cognitive function with alterations of the brain and the exact nature of these alterations is not completely understood. Neuroimaging studies using functional magnetic resonance imaging (fMRI) have documented altered brain functional connectivity in PD^{17,18}. Relative to non-disabled adults, people with PD showed reduced functional connectivity in mesolimbic-striatal and corticostriatal loops, with strengthened connectivity between cortical areas, such as pre-SMA and M1. Exercise has been shown to change altered brain functional connectivity, as demonstrated by inducing an increase in cortico-subcortical connectivity and a decrease in cortico-cortical connectivity after cycling training^{19,20}. In addition, it remains to be answered whether physical exercise can also modulate the disease progress in PD. Blood-based α -synuclein and DJ-1²¹⁻²⁴, as well as quantitative electroencephalogram (qEEG)^{25,26} have been demonstrated to be predictive biomarkers related to disease progress and cognition decline in individuals with PD. EEG is a routine test procedure commonly used in clinical neurology and a gross measure of neural electric activities from the scalp. Amplitude of a given activity reflects the degree of neuronal synchronization underneath the recording lead. The relative magnitude distribution among different frequency bands reflects the brain status whether in sleep, relaxation or vigilance. In addition to the epileptic spikes found in seizure patients, individuals with different mental disorders often have different patterns in their EEG profile. More recent studies in conjunction with other neural imaging measures have shown that EEG may predict the state energy metabolism in the brain as well as how the cognitive information is processed. The characteristics of EEG resonance were further found to be closely associated with how cognitive information is encoded in the brain²⁷. Significant deviation of the alpha EEG (8-12 Hz) from the norm was found in various illnesses. Quantitative EEG is a non-invasive, information rich, and easy-to-use objective test. Recent studies have demonstrated that it is sensitive to detect minor neurological changes. Exploring the changes in biomarkers following physical training will provide more insights into potential mechanisms underlying training-induced benefits in PD. We expect that EEG changes will be seen along with physical and cognitive changes.

The SMARTfit (https://smartfitinc.com/) is a novel technology that provides an opportunity to combine physical training with cognitive training. SMARTfit technology focuses on providing a multi-sensory approach for exercise by simultaneously using visual and auditory stimuli/feedback while delivering physical and cognitive training games. SMARTfit intends to design physical training with game technology by using time and score to ignite engagement and enjoyment during physical training, as well as providing cognitive challenges. In consideration of the imbedded cognitive and motivational components in SMARTfit, it can be utilized as a model to investigate the benefits of combining cognitive challenges with physical training on individuals with PD. Thus, the purpose of this pilot study is to investigate the effectiveness of a SMARTfit training in individuals with PD. Our hypothesis is that SMARTfit training will promote motor and cognition improvements over conventional physical training by altering brain functional connectivity. To test the hypothesis, individuals with mild PD will receive both SMARTfit training and conventional physical training in a counterbalanced order with a washout

SMARTfit Version date: 01/29/2018

period. For each training program, participants will receive a 1-hour training session 3 times per week for 8 weeks. The changes in disease biomarkers before and after training will also be explored.

Parkinson's disease: Approximately 630,000 people in the US were diagnosed with Parkinson's disease (PD) in 2010 and it is estimated that PD prevalence will double by 2040²⁸. PD progression leads to decreased independence and quality of life, as well as increased reliance on the healthcare system. The economic impact of PD, including treatment, social security payments, and lost income from inability to work, exceeded \$14.4 billion in 2010²⁸. There is no known cure for this degenerative disease that results in progressive deterioration of motor skills along with reduced sensory and cognitive function. The current treatment for PD is medication (levodopa, dopamine agonists) and surgical intervention (deep brain stimulation). These treatments only partially treat the symptoms and are less effective over time. Furthermore, they often have undesirable side effects. In the past 15 years, mounting evidence has shown that exercise can ameliorate PD symptoms. Even though exercise has been demonstrated to be beneficial for improving PD motor symptoms, significant gaps in this knowledge limit the ability to create specific exercise prescription to optimize neuroplastic changes in the PD brain¹⁶.

2.0 OBJECTIVES AND PURPOSE

The aims of this pilot study are:

- to examine the changes in clinical and physical performance measures after SMARTfit training and conventional physical training. Outcome measures will include MDS-UPDRS III (motor) score and the modified Physical Performance Test (mPPT) before and after SMARTfit training and conventional physical training. We hypothesize that clinical and physical performance will improve after SMARTfit training more than after conventional physical training.
- 2) to examine the changes in cognitive function measures after SMARTfit training and conventional physical training. Outcome measures will include Trail-Making test (TMT) and Parkinson's Disease-Cognitive Rating Scale (PD-CRS) before and after SMARTfit training and conventional physical training. We hypothesize that cognitive function will improve after SMARTfit training more than after conventional physical training.
- 3) to examine the changes in brain connectivity after SMARTfit training and conventional physical training. Functional magnetic resonance imaging during rest and a cognitive task will be measured before and after SMARTfit training and conventional physical training. We hypothesize that cortico-subcortical connectivity will increase and cortico-cortical connectivity will decrease after SMARTfit training more than after conventional physical training.
- to examine the changes in biomarkers after SMARTfit training and conventional physical training. Blood-based α-synuclein and DJ-1, as well as quantitative EEG will be measured before and after SMARTfit training and conventional physical training.

3.0 STUDY DESIGN

3.1 Methods

Sample size and participants

This pilot study aims to investigate the effects of 8-week SMARTfit training versus conventional physical training on motor function, cognition and brain functional connectivity in individuals with PD. The target sample size is a maximum of 12 participants with PD. Recruitment to this study at this time is based primarily on word of mouth from prior participants. We will also recruit through the use of flyers posted on campus and its immediate vicinity, and through a website. All eligible recruits will sign a written informed consent to participate in the experimental protocol approved by the Institutional Review board of the University of Southern California. All participants will be screened for inclusion and will be excluded from the study if they do not meet the inclusion criteria.

Prior to their arrival, participants will complete one brief (about 5 minutes) intake questionnaire that includes questions about their medical and psychiatric history and their current use of alcohol, nicotine and prescription or non-prescription drugs to screen their eligibility for MRI. The purpose of the interview is to obtain more detailed information about any factors that may influence either their eligibility to participate in the procedures or the results of the procedures themselves. Potential subjects will also be screened for contraindications for MRI experiment such as pregnancy, pacemakers and implants.

Procedures and tasks

This pilot study is a cross-over trial to estimate the effects of 8-week SMARTfit training versus conventional physical training on behavior, brain measures and biomarkers in individuals with Parkinson's disease. Participants will receive both 8-week SMARTfit training and 8-week conventional physical training with an 8-week washout period in between. The order of received training will be counterbalanced between participants. Each training regimen will consist of 24 training sessions over an 8-week period (3 days/week). Motor function, cognitive function, the Unified Parkinson's Disease Rating Scale (UPDRS) measures and functional connectivity of the brain will be assessed before and after each training program.

• MDS Unified Parkinson's disease Rating Scale (UPDRS): The UPDRS is an assessment of Parkinson's disease severity and progress. The UPDRS has four sections. The first section assesses mentation, mood, and behavioral changes. The second section assesses historical activities of daily living. The third section is the motor examination portion of the UPDRS and includes evaluations of tremor, rigidity, bradykinesia, gait, and postural instability. The fourth section evaluates complications of therapy including motor fluctuations and dyskinesias. A 5-point scale is used a well-defined criterion. The UPDRS will be administered by a blinded research investigator who has been trained using the Movement Disorders UPDRS training videos. The UPDRS has universal acceptance as a rating scale for individuals with PD and it has been shown to be reliable and valid. This measure will be used to determine symptom severity. MDC will be 2.5 points between baseline and post-training.

• Modified Physical Performance Test (mPPT): The mPPT is a 9-item test that assesses multiple dimensions of physical function (basic and complex activities of daily living) with different levels of difficulty. This measure correlates well with degree of disability, loss of independence, and early mortality. It is also significantly correlated to UPDRS III and Hoehn and Yahr scale in PD. It is a reliable measure with a high interand intra-rater reliability. Standard instructions will be given to ensure reliability. Participants will be asked to complete functional tasks (i.e. writing a sentence, simulated eating, lift a book and put it on a shelf, turning 360 degrees, 50-foot walking test, stair climbing etc.). Participants' performance will be videotaped and the score of each task will be rated based on the completion time.

• Self-Efficacy for Exercise (SEE) scale: The SEE is to capture an individual's confidence in their ability to continue exercising in the face of barriers to exercise. The SEE consists of 9 items describing potential barriers to participation in exercise (eg, "too busy with other activities," "did not enjoy exercise," "felt pain with exercise," "bored by the exercise"). For each item, participants circled a number from 0 ("not confident") to 10 ("very confident") that best described their belief that they could exercise 3 times a week for 20 minutes. Reliability, validity, and internal consistency have been established for the SEE.

• Quotient test: The Quotient test is an innovative device that objectively measures three domains of cognition: hyperactivity, inattention and impulsivity. This easy-to-administer tool uses advanced motion tracking technology to track micromovements while participants complete a computerized test that takes less than half an hour. Below is an example of the cognitive task involved, it consists of a simple go/no go task which is generally used to clinically assess frontal lobe function. After the test is completed, patterns of motion, accuracy of the responses, and fluctuations in attention state are quickly analyzed and scored using proprietary algorithms based on 19 or more parameters. The motion detection includes 6 movement metrics. The Attention Response Analysis

includes measures of accuracy, omission errors, commission errors, latency, variability, and response time variability. Data for each patient is compared to age and gender matched cohorts. Scores and test data provide both the existence of related deficits and the magnitude of those deficits. Quotient is cleared by the FDA with the intended use to provide objective measures of hyperactivity, impulsivity and inattention to aid in the clinical assessment.

• Trial-Making Test (TMT): The Trail Making Test is a neuropsychological test of visual attention and task switching. It consists of two parts in which the participant is instructed to connect a set of 25 dots as quickly as possible while still maintaining accuracy. The test can provide information about visual search speed, scanning, speed of processing, mental flexibility, as well as executive functioning.

• Parkinson's Disease-Cognitive Rating Scale (PD-CRS): The PDCRS is is a valid, reliable and useful neuropsychological battery designed to cover the full spectrum of cognitive defects associated with PD. The PD-CRS includes 10 'subcortical-type' items (attention, working memory, Stroop test, four verbal fluencies, immediate and delayed verbal memory, clock drawing), and two 'cortical-type' items (naming, copy of a clock). Total score ranges from 0 to 204, subcortical score from 0 to 174, and cortical score from 0 to 30, with higher scores indicating a better functioning.

Magnetic resonance imaging (MRI) protocol

All participants will be screened using the MRI screen questionnaire. The MRI scans will be performed at the Stevens Neuroimaging and Informatics Institute at the USC Health Sciences Campus. Participants will undergo MRI tests at 4 time points (baseline, 8 weeks, 16 weeks and 24 weeks).

MRI preparation and procedures

Participants will be instructed in a behavioral task that they will be asked to do as part of a functional imaging study. In some cases, they will go through sample trials of the task as part of a familiarization period. The participants will then be asked to lie on the bed of the MRI scanner and will be given headphones and ear-protectors. In some cases, a comfortable head restraining device (such as cloth tape or pads on the sides of the head) may be used to reduce excess head motion. The duration of the MRI procedure will be 1 hour. The participants will lie with their head motionless and either relax passively or perform the required behavioral task.

The MRI equipment makes a variety of noises during scanning from repetitive tapping to beeping noises. Anyone in the scanner room while the scanner is in operation must use hearing protection in the form of earplugs and/or headphones to avoid hearing injury from the acoustic noise generated by the scanner. The earplugs and/or headphones provided reduce the noise levels to a level comfortably below the FDA guidelines. The scanners are equipped with a squeeze bulb that allows the participant to set off an audible alarm to attract the operator's attention. The squeeze bulb will be made available to participants. After completion of the imaging, the participant will be removed from the instrument. We interview the participants informally for any adverse or unexpected

reactions that may have taken place during the study.

Blood oxygen level dependent (BOLD) functional MRI (fMRI): fMRI is one of the most widely used MRI techniques for studying human brain function. Since the seminal discovery of functional connectivity (FC) between distributed brain areas during the resting state, resting state fMRI (rs-fMRI) has become a major tool for characterizing the dynamic organization of large scale brain networks. With the recent development of simultaneous multi-slice (SMS) or multiband imaging, whole brain BOLD fMRI using gradient-echo echo-planar imaging (GE-EPI) can be performed with an isotropic spatial resolution of a few mm³ and a temporal sampling rate of a few hundred milliseconds per volume, as demonstrated by the Human Connectome Project (HCP²⁹). At ultrahigh magnetic fields, fMRI with a sub-millimeter spatial resolution has been applied for studying human brain function at the cortical layer or column level. Each test session consists of fMRI during a cognitive task and at resting state.

- Task-based fMRI: Participants will perform a word-color Stroop paradigm that has been previously • adapted for use in fMRI experiments³⁰. The task is composed of two conditions: congruent and incongruent, interspersed with periods of no stimuli (baseline). The visual stimuli consist of four words: red, blue, green and yellow. In the congruent condition, words appear in their matching colors, whereas in the incongruent condition, the colors do not match their content. Participants will be instructed to press the buttons as quickly as possible according to the color of the ink presented while disregarding the meaning of the word. Responses will be made using the index and middle finger of both the left and right hand using a response box that contained four buttons. The same number of stimuli is given to the left and right hand. The color of the four buttons is presented on the top of the computer screen. Stimuli will be presented at a rate of 1 sec for color word interleaved with 2 sec of a blank screen. Each task block contains 12 different words of which 1/3 are distracters (congruent in incongruent trials and vice versa), interleaved with a 10 sec baseline which consists of a red fixation point at the center of the screen. There are seven alternating blocks of the two conditions (four incongruent and three congruent) and eight baseline blocks. For all participants, adequate task performance will be assured by familiarization and practice of the task prior to entering the MRI scanner.
- Resting state fMRI: Participants will be instructed to keep their eyes open fixation on a projected image of a white cross on a black background, to remain motionless, and to not to think of anything in particular. The scanning session will last for 6 mins.

Quantitative electroencephalogram (qEEG) protocol

A 19-channel EEG acquisition system (Deymed Diagnostic, TruScan 32) will be used in recording. Participants will be instructed to sit quietly with eyes closed whilst wearing a skull cap. An electrode cap designed according to standard International 10-20 Montage system is placed over the head with proper skin preparation to ensure each electrode is well contacted (impedance < 5k). Ten minutes of rest data will be collected. Data will be amplified and digitized at 512 point/c and stored on a computer hard disk for off-line analysis.

Blood sample collection protocol

A venous blood sample of up to 40 ml will be obtained from participants. The amount drawn from participants will not exceed the lesser of 50ml or 3ml per kg of the participant's weight in an 8 week period.

Training program

All participants will receive the following trainings with a counter-balanced order. Training sessions will take place at the Division of Biokinesiology and Physical Therapy (CHP building).

- (1) SMARTfit training
- (2) Conventional physical training.

For both SMARTfit training and conventional physical training, participants receive three 1-hour training sessions per week for 8 weeks. During each week, participants will receive physical training focused on six tasks, which are the functional tasks individuals with PD commonly have difficulty with. The six tasks are paired into 3 pairs (see Table 1). Participants will focus on practicing one pair of tasks during each session.

Table 1. Functional task training

Table 1. Functional task training				
Pair Task 1	Task 2			

	1	Sit-to-stand	Multi-plane locomotor tasks (obstacle course)
Ī	2	Gait	Reach & Grasp
	3	Floor-to-stand; Stand-to-floor	Single limb standing

For each of the trained task, the five components (movement amplitude/speed; endurance; balance; vision; accuracy) can be manipulated to scale up and down based on each participant's capability. Each component has three difficulty levels. Please see Appendix 1 for the details of three difficulty levels for each component. This provides the training therapist a standardized guideline to adjust the task difficulty to fit each participant's priority and participants' progress over 8 weeks to make sure that each training session is at the optimal challenge point in order to maximize the effect of training³¹. For the SMARTfit training, there is an additional cognition component that can be manipulated using features provided by SMARTfit. After each training session, participants' rating of perceived exertion (RPE) will be obtained using a 1-10 Borg scale. Participants' RPE should be between 6 to 8. If the participant's RPE exceeds 8, then in the next training session the challenge level of trained task will be scaled down until they are at or below 8 on the Borg scale. At any point during the session, participants are allowed to terminate by telling the researcher that they would like to stop.

3.2 Dependent measures

Primary outcome measure

1. Modified Physocal Performance Test score (mPPT)

Secondary outcome measures

- 1. UPDRS score
- 2. Self-Efficacy for Exercise scale (SEES)
- 3. Trail-making test (TMT)
- 4. Parkinson's Disease-Cognitive Rating Scale (PDCRS)
- 5. Quotient system test
- 6. Functional connectivity
- 7. Quantative EEG measures
- 8. α-synuclein and DJ-1

3.3 Data processing

Statistical Parametric Mapping will be used to process the fMRI data. The fMRI analysis focuss on the whole brain. An inclusion criterion for fMRI image analysis is head motion < 2 mm in any direction. The functional images are subjected to geometric distortion (field map) correction and motion correction. The structural images will be co-registered to the mean unwarped and motion corrected functional image for each participant and functional and structural images will be normalized to Montreal Neurological Institute (MNI) space. Functional volumes will be smoothed with a Gaussian kernel of 8 mm3 (FWHM). Correlational analyses between the BOLD signal from an a priori selected seed and every other brain voxel during the entire acquisition condition will be run to provide seed-to-voxel connectivity estimations for each participant. Movement parameters will be entered as first-level covariates in the model. Before averaging individual voxel data, the waveform of each brain voxel will be filtered using a bandpass filter to reduce the effect of low-frequency drift and high-frequency noise. Several sources of spurious variance along with their temporal derivatives will then be removed from the data through linear regression: signal from movement, signal from ventricular regions, and signal from the white matter. Because further steps include between-sessions comparisons, temporal connectivity maps will be generated for each participant across the conditions. These images will be then included in a second-level analysis.

EEG will be recorded using Deymed acquisition system and then converted to *.EDF format for offline analysis. Raw data will be carefully inspected and edited to reject all movement artifacts. Total of 4-min artifact free epochs will be included in the quantitative analyses. All data will be analyzed by a fast Fourier transform routine using 1,024 point FFT window to yield a power density spectrum for each channel. According to clinical EEG convention, power density will be calculated at the following frequencies: delta (<4Hz), theta (4-8Hz), alpha (8-12Hz), and beta (12-30), respectively. In addition to fast Fourier transform, we will calculate cross-channel correlation in time domain, coherence in frequency domain and power density mappings. A contour map will also be generated for each frequency band using the nearest neighbor algorithm. NBRL NeuroRef, which applies LORETA technology to convert EEG voltage signals into current density, will be applied to map out the distribution in 3-D space by overlapping with a morphed MRI image. Individual's data will be further analyzed and compared with an FDA approved normative EEG database licensed from NYU to determine degrees of deviation of respected variables from the norm. Multivariate discriminant function analysis will be used to determine degrees of deviation of individual's data from norm by linear composite of variances from the means of

database. Z-scores will be calculated for the following measures: (1) absolute power of all frequencies in all channels, (2) relative power of all frequencies in all channels, (3) mean frequency of alpha rhythm in all channels, (4) 19 X 19 coherence matrix and mappings for each frequency, and (5) 3-D current density mappings for interested frequency using sLORETA technology. Results of analyses will be exported to a spreadsheet for further statistical analysis.

Blood samples labeled with participant ID will be frozen and shipped to the Laboratory of Molecular Psychiatry at University of California, Irvine for data processing and analysis. Alpha-synuclein and DJ-1 levels will be measured using an established protocol in previous research³².

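### The one connectivity pipeline has no step for the Stroop block response, so on the task run it can report shared activation as connectivity

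*Combined protocol and SAP*

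**What the plan says.** Aim 3 in section 2.0 rests on two kinds of scan: "Functional magnetic resonance imaging during rest and a cognitive task will be measured before and after SMARTfit training and conventional physical training". Its hypothesis is directional and comparative: cortico-subcortical connectivity up and cortico-cortical connectivity down, more after SMARTfit than after conventional training.

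The task-based fMRI text in section 3.1 makes the Stroop run a block design: "There are seven alternating blocks of the two conditions (four incongruent and three congruent) and eight baseline blocks". Each task block has 12 words, each shown for 1 s and followed by a 2 s blank; each baseline lasts 10 s.

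Section 3.3 describes one connectivity pipeline. For each participant, the seed is correlated with all other voxels "during the entire acquisition condition". Of covariates it says "Movement parameters will be entered as first-level covariates in the model". The time course is "filtered using a bandpass filter to reduce the effect of low-frequency drift and high-frequency noise", with no cut-offs. The spurious sources regressed out, with their temporal derivatives, are "signal from movement, signal from ventricular regions, and signal from the white matter". Then "temporal connectivity maps will be generated for each participant across the conditions", and the maps go to a second-level, between-session comparison. No task regressor, block-wise analysis, residual-connectivity step or psychophysiological-interaction term appears.

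**The concern.** A seed correlation over a whole block-design run mixes two things: fluctuations that two regions share because they are coupled, and the rise and fall that each shows because the task switches on and off. If the second part stays in, regions that respond to the task correlate even when nothing links them, and a change in response size appears as a change in connectivity.

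This matters because SMARTfit adds a cognition component that conventional training lacks (section 3.1, Training program). Training could plausibly change Stroop activation, and by different amounts after the two programmes. The repeated measures ANOVA in section 13.0 works on the resulting measure and cannot separate activation from coupling. Section 13.0 also says the data will be used to estimate effect sizes for later studies, so a bias could carry forward.

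**Working it through.** The plan gives no figure on this point, so there is none to reproduce.

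**1. Timing (section 3.1).**
- Task block: 12 × (1 + 2) s = 36 s.
- Run: 7 × 36 + 8 × 10 = 332 s, of which 80/332 = 24% is baseline.
- On/off cycle: 36 + 10 = 46 s, or 1/46 = 0.022 Hz.
- Incongruent/congruent cycle: 92 s, or 0.011 Hz.

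**2. Does the filter remove it?** The cut-offs are not stated. I assumed four usual bands (0.008–0.09, 0.01–0.10, 0.009–0.08 and 0.01–0.08 Hz) and a double-gamma haemodynamic response (HRF). Between 98% and 99% of the block-response variance lies inside these bands. A second-order Butterworth filter with gradual edges keeps 0.946 to 0.983 of its standard deviation, so 0.946² = 89% to 0.983² = 97% of its variance. The filter is no safeguard.

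**3. Size of the induced correlation.** Let A and B be the shares of in-band variance that the block response explains in seed and voxel, and ρ the true coupling of the remainder. For same-sign responses:

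r = ρ√((1 − A)(1 − B)) + √(AB)

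The second term changes sign if the responses are opposite. The shares are assumptions; the documents give none. With ρ = 0:

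| Seed share | Voxel share | r |
|---|---|---|
| 0.10 | 0.10 | 0.10 |
| 0.20 | 0.20 | 0.20 |
| 0.30 | 0.30 | 0.30 |
| 0.20 | 0.05 | √0.010 = 0.10 |
| 0.30 | 0.05 | √0.015 = 0.12 |
| any | 0 | 0 |

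Simulation of the 332 s run agrees: about 0.10, 0.20 and 0.29 to 0.30 for the equal shares.

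**4. False change.** If both shares rise from 0.20 to 0.30 with no coupling, r rises by 0.10. If only the seed rises and the voxel stays at 0.05, r rises by 0.12 − 0.10 = 0.02. With true coupling fixed at 0.30, equal shares moving from 0.20 to 0.36 take r from 0.30 × 0.80 + 0.20 = 0.44 to 0.30 × 0.64 + 0.36 = 0.55, a gain of 0.11. With no coupling the same move gains 0.16.

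**5. After task regression.** With block regressors that match the response, mean r returns to the true value: −0.01 to 0.01 for ρ = 0 and 0.29 to 0.30 for ρ = 0.30. If the true response lags the assumed one, two regressors leave some bias. A 2 s lag leaves r of 0.02, 0.04 and 0.06 for equal shares of 10%, 20% and 30%; a 3 s lag leaves 0.04, 0.07 and 0.13. Adding temporal derivatives takes out most of that remainder.

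**The case against.** **The Stroop run is not named.** Section 3.3 speaks of an acquisition condition, and section 3.1 uses conditions for congruent and incongruent blocks. A reader might infer that the plan expressly commits to correlating over the whole Stroop run; it does not. Under a condition-wise reading the on/off component shrinks. Keeping only samples where the unfiltered modelled response exceeds 0.9 of its plateau (65% of the run) leaves 0.12 of its standard deviation, about 1.4% of its variance. The ambiguity therefore stands. But this is the only pipeline given, aim 3 includes the task scan, and no reading supplies an explicit step for the blocks.

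**Task-state connectivity may include evoked fluctuation.** Aim 3 does not define its measure as residual or background connectivity, so a reader should not conclude that a whole-run correlation is meaningless. What stands against the plan is that such a correlation cannot tell changed coupling from changed activation, and the plan does not say that it accepts this.

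**The hypothesis is a contrast.** A reader might infer that a change in activation alone would confirm or refute aim 3. The documents do not support that. Change common to both trainings largely cancels in this counterbalanced crossover. A uniform same-sign rise in activation would push both connectivity types up, whereas aim 3 predicts opposite directions. Part of the pattern could be biased, but the whole would not be reproduced.

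**The illustration is a favourable case.** Equal, same-sign shares give the larger figures; step 4 of the working shows how fast they fall otherwise. This objection stands in full.

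**Conclusion.** The concern holds in a limited form. Applied to the Stroop run, which is the natural reading, the pipeline in section 3.3 leaves the block response in the seed correlation. The induced correlation is roughly √(AB), positive or negative with the sign of the responses: 0.10 to 0.30 for equal shares of 10% to 30%, less when one region responds weakly, and zero when one does not respond. These sizes rest on assumed shares, filter cut-offs and response shape.

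The consequence is possible bias in the task-run part of aim 3, and only where activation changes differently after the two trainings. It does not reach the resting scan, nor the primary mPPT outcome; functional connectivity is the sixth of eight secondary outcomes in section 3.2. It would also be wrong to assume that rest and task runs are already planned as separate analyses, because no section says so. The correction is cheap and should be made before the Stroop data are analysed.

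**What to change.** In section 3.3:

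- For the Stroop run, add HRF-convolved congruent and incongruent block regressors and their temporal derivatives, filtered identically to the data, to the nuisance regression before the seed correlation.
- If the question is instead how connectivity differs between incongruent and congruent blocks, prespecify a psychophysiological-interaction model that includes the task main effects. This answers a different question from residual connectivity, so the plan should say which one aim 3 asks.
- State that rest and task runs are analysed separately, name the run behind each map, and give the bandpass cut-offs.
- Report Stroop activation separately, so that a change in response can be seen alongside any change in connectivity.

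No new data are needed. The cost is a few degrees of freedom per run: two block regressors and two derivatives make four. A mismatch between the assumed and true haemodynamic response may leave a small residual bias.
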